9.8 RPCA item details

9.8.1 AYA Version (not included in parent surveys)

9.8.1.1 Hospital Anxiety and Depression Scale (HADS). The HADS assesses mixed affective symptoms in patients with serious illness.¹ It has been validated in AYAs with chronic illness¹⁰⁵ as well as AYA cancer survivors.¹⁰⁶ The scale has excellent reliability ($\alpha=0.83-0.82$).¹ It consists of 7 questions for anxiety and 7 for depression. Each is scored from 0-3, for a total range of 0-21 points per subscale. “Caseness” of anxiety and depression is defined as ≥ 8 points, with sensitivity/specificity of 0.8/0.9 for anxiety and 0.8/0.8 for depression.¹ This instrument will be included in the full (non-abbreviated) RPCA survey as well as the 3 and 6 month shortened RPCA.

9.8.1.2 Memorial Symptom Assessment Scale (MSAS). The MSAS measures the presence, severity, frequency, and extent of bother from 26 symptoms with high consistency ($\alpha>0.8$).^{2,107} For this study, we will use a version of the MSAS that has been previously developed for and used among children with advanced cancer.^{98,108} Likert scales assess physical (pain, fatigue, drowsiness, nausea, anorexia, cough, diarrhea, vomiting, itching, skin issues, constipation, dysphagia, dry mouth, numbness, sweating, dyspnea, and dysuria), and psychological (irritability, sleep disturbance, nervousness, sadness, worrying, difficulty concentrating, and image issues) symptoms. Total- and sub-scores are calculated as an average, with higher scores representing higher symptom burden. This instrument will only be included only in full (non-abbreviated) RPCA surveys.

9.8.1.3 Pediatric Quality of Life (PedsQL) Generic and Cancer Module Teen Reports. The PedsQL 4.0 Generic and 3.0 Cancer Module include 50 items evaluating HRQOL of AYAs with cancer. Queries assess physical, emotional, social, and school well-being, plus cancer-related pain and hurt, nausea, procedural anxiety, treatment anxiety, worry, cognitive problems, perceived physical appearance, and communication. Scales are available for teens and young adults,^{3,4} and have been used successfully with low rates of refusal and minimal missing data.¹⁰⁹ Items are rated on a 5-point Likert scale and total scores transformed to a 0-100 scale with higher scores representing better HRQOL. Internal consistency ranges from 0.75 to 0.92.⁴ This instrument will only be included only in full (non-abbreviated) RPCA surveys.

9.8.1.4 Hope Scale. The Snyder “Hope” Scale contains 8 hope items plus 4 “filler” questions, and measures “the overall perception that one’s goals can be met.”⁵ The instrument was named based on patterns of hopeful thought and assesses patient-reported efficacy by assessing the ability to generate a route to one’s goals (termed “pathway” thoughts) and the ability to initiate and maintain the actions necessary to reach a goal (termed “agency”

thoughts). Prior studies performed among AYA cancer patients have shown that high-hope individuals have improved psychosocial outcomes. The instrument has been validated in both adult and pediatric settings and is scored on an 8-point Likert scale. Higher scores imply greater levels of hopeful thought patterns. Cronbach's alphas for the whole scale range from .74 to 0.84. This instrument will only be included only full (non-abbreviated) RPCA surveys.

9.8.1.5 Connor-Davidson Resilience Scale. The Connor-Davidson Resilience Scale (CD-RISC) is a reliable and widely used instrument to measure inherent resiliency.⁶ Questions revolve around personal problem-solving and approaches to adversity. The 10-item instrument has high internal consistency (Cronbach's alpha = 0.85), and has been used in diverse populations including adolescents, parents and cancer patients.^{6,110} Correlative studies have evaluated the scale with other psychosocial measures such as psychological distress,¹¹¹ PTSD,¹¹² and social support.¹¹³ It also has been used in pharmacologic and other intervention studies to model modifiable outcomes. Each item consists of a 5-point Likert scale (scored from zero to four) for total of 40 points. The mean score among well US adults is 31.8, with higher scores reflecting greater resilience. This instrument will only be included only full (non-abbreviated) RPCA surveys.

9.8.2 Both AYA and Parent Version

9.8.2.1 Health Utilities Index (HUI). The HUI is a multi-attribute preference-based health-status classification system validated in AYA cancer populations.¹⁰⁰⁻¹⁰⁴ The index consists of 15 total queries to assess 2 systems - cognition, emotion, fertility, mobility, pain, self-care, and sensation (HUI2); and, ambulation, cognition, dexterity, hearing, emotion, pain, speech and vision problems (HUI3). Scoring is based on standard gamble utilities, with scores from 0 (health-state preference equivalent to death) to 1 (perfect health). Parents will be asked to complete the survey as a proxy for their AYA participant. Patient data will be used unless unavailable; only in cases where patient data is unavailable will parent proxy data be used for data analysis. This instrument will be included in the full (non-abbreviated) RPCA surveys as well as the 3 and 6 month shortened RPCAs.

9.8.2.2 The COVID-19 Impact Questionnaire. (COVID-IQ) This 7-item, self-report questionnaire was developed for this study to assess perceived impact of the COVID-19 pandemic on AYAs and parents. Items assess worry/anxiety related to COVID-19, life events as a result of COVID-19 (e.g., loss of job, missed school), lifestyle changes (e.g., social distancing), and known COVID-19 symptoms/diagnoses/treatments of self and family members. Respondents are invited to provide free text responses for two additional items: 1) "What is helping you through the COVID-19 pandemic" and 2) "Please tell us about other effects of COVID-19 on yourself, your child(ren) and/or your family, both negative and/or positive." Lastly, respondents are

asked to rate the extent to which their responses to other survey questionnaires were impacted by the COVID-19 pandemic. This instrument will be included in the patient and parent RPCA surveys.

9.8.3. Parent Version (not included in AYA surveys)

9.8.3.1 Generalized Anxiety Disorder Screener (GAD-7). This 7-item survey is commonly used to identify cases of generalized anxiety disorder and to assess symptom severity.^{9,114} Participants are asked how often during the last two weeks they have been bothered by each of the 7 core symptoms of generalized anxiety disorder. Response options include "not at all," "several days," "more than half the days," and "nearly every day," scored as 0, 1, 2, and 3, respectively. Therefore, GAD-7 score range from 0 to 21, with scores of ≥ 5 , ≥ 10 , and ≥ 15 representing mild, moderate, and severe anxiety symptoms levels, respectively. Internal consistency was acceptable ($\alpha=0.89$). Inter-correlations ranged from $r = 0.45$ to $r = 0.65$. This instrument will only be included only full (non-abbreviated) RPCA surveys.

9.8.3.2 Patient Health Questionnaire (PHQ-8). This 8-item survey is widely used among general populations, patients with chronic illness, and in parents of children with cancer.^{10,11,115-118} It is identical to the also widely used PHQ-9, with the exception that PHQ-8 deletes a question about suicidal ideation. Research indicates that the deletion of this question has a minimal effect because self-harm thoughts are relatively rare and this item is the least commonly endorsed item on the 9-item survey. Furthermore, the original validation studies of the two instruments demonstrate similar psychometrics and identical thresholds for depression severity. The instruments have excellent psychometric properties ($\alpha=0.86-0.89$). Each item is scored on a 4-point Likert scale and the sum (0-27) indicates the degree of depression, with scores of ≥ 5 , ≥ 10 , and ≥ 15 representing mild, moderate, and severe depression. Scores correlate with functional status and are sensitive to behavioral interventions.^{118,119} This instrument will only be included only full (non-abbreviated) RPCA surveys.

9.8.3.3 Medical Outcomes Study 36-item Health Survey (SF-36). The SF-36 is the most widely used generic measure of HRQOL among U.S. Adults.⁸⁰ It incorporates 8 concepts: physical functioning, body pain, limitations due to physical health problems, role limitations due to personal or emotional problems as well as emotional well-being and social functioning, energy, fatigue and general health perceptions. It includes a single item regarding perceived change in health.⁸ Internal reliability ranges from $\alpha=0.78-0.93$. This instrument will only be included only full (non-abbreviated) RPCA surveys.

9.8.3.4 Hospital Consumer Assessment of Healthcare Providers and Systems (HCAHPS). This survey is a widely used and standardized tool to measure patient and family perspectives on hospital care.¹² It has been endorsed by the National Quality Forum (NQF) in order to allow for cross-hospital

comparisons. The survey includes a core set of questions that can also be combined with customized project- or site-specific items. For this study, we have included a small subset of questions from domains regarding care for teenaged patients, communication and child-centered care, and overall hospital ratings. All items are scored on a Likert Scale (for example, to the question "During this hospital stay, how often did providers involve your child in discussions about his or her health care?" response options include "Never," "Sometimes," "Usually," and "Always." This instrument will only be included only full (non-abbreviated) RPCA surveys.

9.8.3.5 Patient costs. A study-specific cost-of-care checklist was adapted from consensus guidelines for cost-effectiveness analyses.⁷⁸ It will be embedded within RPCA surveys and query parent-estimates of: (1) direct costs: time costs (travel/wait time, time with providers), out-of-pocket expenses (gas/travel, other child-care needs); (2) indirect costs: time-lost from vocation or employment (see appendix). It will be included in the full and abbreviated surveys (RPCA, aRPCA and the 3 and 6 month shortened RPCA) in order to minimize recall bias and accurately collect monthly costing data from then perspective of parent/guardian caregivers. Due to recall bias, parents will be able to complete this questionnaire in real time over the course of the month. Parents will be given the questionnaire at the beginning of each month to have on hand to complete. If parents do not fill it out in real time, they will have the chance to complete in based on recall during their monthly visit in their embedded RPCA/aRPCA

9.9 Optional Procedures

9.9.1 Heart Rate Variability Data Collection

HRV will be measured using the Actiheart 5 external device (CamnTech, Inc, UKFDA class 2, 510(k) number K052489). The Actiheart 5 is an FDA-approved, lightweight, wireless electrocardiogram (ECG) monitor that attaches to a patient's torso via two standard ECG electrodes. Patients who consent to the optional HRV measurement portion of the study will be given their Actiheart monitor at enrollment. A study team member (licensed medical provider or CRA with appropriate certification, per site requirements) will place the monitor on the patient (left chest) and ensure adequate ECG signal acquisition OR a study CRA will instruct the patient (no physical patient contact from CRA). The patients will wear the monitor for a 24h period, and then return the device to a study team member. The devices will be collected at the next planned clinic appointment if outpatient, or the next day if inpatient.

9.9.2 Blood Samples

Whole blood samples will be sent to the University of California Los Angeles (UCLA) Social Genomics Core for transcriptome profiling using RNA sequencing.¹²⁰ The Clinical Research Associate will work with inpatient or outpatient staff to obtain subject's blood. A total volume of 5 ml of blood will be collected from subjects at the time of any clinical blood draw or intravenous access near the planned study time point. For smaller

children, we will follow clinical guidelines regarding volume of blood draws. Blood samples needed for clinical purposes will be prioritized over research lab collection.

Biospecimens (blood samples) will be temporarily stored in secure freezers at Seattle Children's Hospital Research Lab Services (RLS). The specimens will be labeled only with study identification numbers. Blood samples will be stored until 20 samples have been collected (anticipate <6 months depending on enrollment), and then will be shipped to the UCLA laboratory for analysis. No biospecimens will be banked.

Following quality assurance testing of suitable mass (Nanodrop ND1000) and integrity (Agilent Bioanalyzer RNA Integrity Score), mRNA will be converted to cDNA (Illumina TruSeq), and >10 million sequence reads will be obtained on an Illumina HiSeq 4000 instrument in the UCLA Neuroscience Genomics Core.

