4.0 Study-Wide Number of Subjects

Number of subjects: We will enroll and randomize a total of n=90 AYAs from the four sites in order to reach our target n=70 of evaluable patients with complete data at the primary endpoint (Table 3). Note that both AYA patients and their parents/legal guardians will be enrolled when possible in order to collect accurate costing data. The rationale is that much of the day-to-day costs such as transportation and missed work will be experienced by PARENTS rather than AYAs.

Table 3. Annual number of AYAs (12-24 yrs-old) who are eligible, enrolled, and evaluable at 6 months				
Site	Total	Eligible	Enrolled	Evaluable
SCCA	18	16	11	10
CHLA	12	11	7	6
St. Jude	10	9	6	4
UAB	10	8	6	4
Total/Year	50	44	30	24
Total for 36-month recruitment period:		90		>70

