9.9.3 Data Collection Schedule

HRV data and/or blood samples will be collected at clinically relevant and study specific time intervals where possible (**Table 6**). When not possible, HRV and/or blood sample data collection will be scheduled at the patient's convenience, and/or during the next scheduled clinical lab draw. .

Table 6. Biological data collection schedule

Time Point	T1 (Baseline)	T2 (PRISM session #1 OR 1 week post enrollment)	T3 1 month (survey timepoint)	T4 3 months (survey timepoint)	T5 6 months (survey timepoint)
24-hour HRV Recording	X	X	X	X	X
Blood Sample	X		X	X	

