11.5.4 **We will explore the relationship between biomedical variables and patient reported anxiety and depression** through a combination of paired and unpaired t-tests, chi-squared (or Fisher's exact) tests, and linear and logistics regression. DNE will be defined as the number of days from transplant to an absolute neutrophil count (ANC) of >500/mm³ for >3 days. Cumulative incidence and severity of Grade II-IV GVHD will be defined by the revised Seattle Criteria as documented by the patient's clinical provider. HRV will be measured in 24-hour increments using both time and frequency domain parameters as established by the international Cardiology task force guidelines. Means and standard deviations will be compared to published normative data in adolescents. CTRA scores will be divided into two groups (above and below the median). We will perform multivariable analyses, adjusting for age, sex, diagnosis, disease status at the time of transplant, conditioning intensity, and,

immunosuppressive medications/GVHD prophylaxis to examine the association between CTRA biology and HCT outcomes.

11.6 Additional analyses, confounders, and other considerations.

We will conduct interaction modeling and subgroup analyses to explore whether the effect of the intervention is modified by medical covariates, symptom distress, and/or adherence. The rationale for these subgroup analyses is grounded in prior findings suggesting symptoms, adherence, and overall well-being are associated.¹⁴⁰

We will conduct a thorough process evaluation that includes: (a) intervention fidelity; and, (b) satisfaction queries. Multiple comparisons are a concern since we are collecting multiple measures from patients and are interested in several hypotheses. We minimize this problem by specifying a limited number of main hypotheses for each aim. The Benjamini-Hochberg procedure will be used to control the False Discovery Rate criterion at $\alpha=0.05$ to correct for multiple testing in analyses that are not pre-specified.¹⁴¹ Likewise, in manuscripts and presentations, we will report the number of tests performed and interpret results within this context.

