13.0 Provisions to Monitor the Data to Ensure the Safety of Subjects

13.1 Data collection:

Data collection will occur at each of the enrolling study sites: Seattle Cancer Care Alliance (Seattle Children's Hospital and Fred Hutchinson Cancer Research Center), Children's Hospital Los Angeles (CHLA), University of Alabama at Birmingham (UAB) and St. Jude Children's Research Hospital (SJCRH), with the exception of CTRA gene

expression, which will only be collected at the Seattle site. Data collection will consist of self-report questionnaires and electronic ECG recordings from HRV monitors. Research material collected will be in the form of data from standardized questionnaires, digital ECG files, and also from medical record information extracted from the patient's electronic medical record. Protected health information (PHI) is accessible only by the site PIs and key study personnel.

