13.6 Blood Samples

5 mL whole blood will be collected in a PaxGene (PreAnalytiX GmbH) blood tube at the time of a planned clinical blood draw. These biospecimens will be labeled with the subject's study ID only (no identifying information) and sent to the Seattle Children's Research Lab Services (RLS) Core (Seattle Children's Hospital, Seattle, WA) for storage. De-identified, batched blood samples will be shipped by RLS to the University of California Los Angeles (UCLA) Social Genomics Core Laboratory for analysis.

13.7 Data Collection Procedures/ Internal Site Monitoring plan:

The coordinating center will be responsible for systematic data collection, quality control, and data-management procedures including: (1) oversight of ongoing data collection; (2) rigorous training and ongoing monitoring of adherence to protocols; (3) regular review of questionnaire response rates and missing items to identify and correct problems; (4) verification of all data through computerized data entry systems restricting invalid/out-of-range responses; (5) at minimum monthly meetings and progress reports to provide feedback to study staff concerning difficulties and follow-up to ensure problems are resolved quickly, and (6) yearly on-site monitoring of participating sites.

13.7.1 Survey data:

To optimize collection, all participant surveys will be available by paper or online via the REDCap system, a secure HIPAA-compliant, high-quality data collection tool. The rationale for offering both paper-pencil and electronic versions is based on our prior experience where participants preferred the former,⁹² which in turn facilitated more complete data collection. To ensure primary outcome data, we will offer an abbreviated survey with only the HADS and HUI for those who do not complete all assessments or who request to drop out. To ensure data quality, a RA will review RPCA surveys within 72 hours of their completion for missing fields and call participants to clarify and query/complete individual missing items verbally.

13.7.2 MEMS caps:

One to two weeks following discharge from the initial HCT and the day after any subsequent hospitalizations, an RA will contact the family by phone to review the MEMS-cap system and, where relevant, confirm the MEMS-cap is being used. Where indicated, to identify obstacles and solutions to its use.

13.7.3 Medical record data:

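### CTRA blood is shipped by tube count rather than by patient, so many participants' baseline and 3-month samples would travel in different shipments, and the plan is silent on how batch is handled

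*Combined protocol and SAP*

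**What the plan says.** Section 9.9.2 gives the shipping trigger: "Blood samples will be stored until 20 samples have been collected (anticipate <6 months depending on enrollment), and then will be shipped". The same section adds "No biospecimens will be banked", and section 13.6 repeats the idea: "De-identified, batched blood samples will be shipped by RLS".

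Table 6 in section 9.9.3 schedules three bloods per participant, at baseline, 1 month and 3 months. Section 13.1 limits gene expression with the words "expression, which will only be collected at the Seattle site", and section 3.1 makes the component optional.

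Section 11.5.4 plans paired and unpaired t-tests and regressions for the biomedical variables, divides CTRA scores at the median, and describes a multivariable model of CTRA against transplant outcomes, "adjusting for age, sex, diagnosis, disease status at the time of transplant, conditioning intensity" and immunosuppression or GVHD prophylaxis.

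Sections 9.9.2 and 13.7.5 cover RNA quality checks, mapping and counts per million. Section 21.5 gives the bioinformatics to the external core without describing a method. No section says how shipments map to laboratory batches, keeps one patient's tubes together, or mentions bridging samples, batch correction or a batch variable.

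**The concern.** RNA-sequencing measurements can shift between library-preparation or sequencing batches. Scaling to counts per million corrects for sequencing depth, not for such shifts.

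A trigger of 20 tubes, with three tubes per person spread over three months, will often cut through a person's series. If the two parts are processed separately, that person's change from baseline contains the difference between batches. A single median taken over all scores would also label some people high or low partly because of when their tubes were processed.

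At stake is the interpretability of one exploratory outcome listed in section 1.5.2. The split can be prevented at the design stage at little cost. Once a patient's tubes have been run separately, it cannot be designed away.

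**Working it through.** **Inputs**

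- Tubes per shipment: 20 (section 9.9.2).
- Tubes per participant: 3, at months 0, 1 and 3 (Table 6: "Blood Sample X X X").
- Seattle enrolment, source A: 11 a year (Table 3: "SCCA 18 16 11 10", third figure).
- Seattle enrolment, source B: 50 to 60 in three years (section 25), which is 50/3 = 16.7 to 60/3 = 20 a year. The two sources disagree, since A gives 11 × 3 = 33 in three years, so both are carried through.
- Uptake of the optional component: not given. Assumed 50% to 100%, with 25% as a low case.

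**Step 1: reproduce the plan's own figure.** Months to fill a shipment: L = 12 × 20 / (patients per year × uptake × 3). At full uptake:

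- 11 a year: 240/33 = 7.3 months.
- 16.7 a year: 240/50 = 4.8 months.
- 20 a year: 240/60 = 4.0 months.

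The protocol says "anticipate <6 months depending on enrollment". Source B reproduces this at full uptake; source A does not. Filling 20 tubes in exactly 6 months needs 40/3 = 13.3 participating patients a year.

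**Step 2: share of patients whose month-0 and month-3 tubes are in different shipments.** The approximation is min(1, 3/L). As a check, Poisson enrolment over 36 months was simulated, with draws at months 0, 1 and 3, and tubes were cut in order of collection into groups of 20 (thousands of replicates per scenario).

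| Patients per year | Uptake | L (months) | 3/L | Simulated share split |
|---|---|---|---|---|
| 11 | 100% | 7.3 | 41% | 45% |
| 16.7 | 100% | 4.8 | 62% | 65% |
| 20 | 100% | 4.0 | 75% | 75% |
| 11 | 50% | 14.5 | 21% | 24% |
| 16.7 | 50% | 9.6 | 31% | 35% |
| 20 | 50% | 8.0 | 38% | 41% |

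At 25% uptake the simulated share is about 11% (11 a year) to 21% (20 a year).

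**Step 3: a check without an uptake assumption.** If 20 tubes really do accumulate in under 6 months, then 3/L exceeds 3/6 = 50%. On the protocol's own expectation, about half of participants or more would be split.

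**Step 4: how far shipment lines up with visit overall.** Enrolment is staggered, so most shipments mix visits. In the simulation at full uptake, baseline tubes are 41% to 46% of the first shipment and 10% to 16% of the last, against 33% overall. The alignment is strongest at the two ends of accrual.

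**Step 5: number of shipments.** At full uptake the simulation gives about 5 (11 a year) to 9 (20 a year) over 36 months. A fixed batch factor would therefore use about 4 to 8 parameters.

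These steps measure how often a series is split. They do not measure the size of any batch shift, for which the documents give no figure.

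**The case against.** The strongest objection is that a shipment is not a sequencing run. Section 9.9.2 says when tubes leave Seattle, not when libraries are made or sequenced. The external core could pool shipments or correct for batch. Repeated shipping is itself inferred: the rule is stated once, although batched shipment and the absence of banking fit repetition. This stands, and it makes the concern conditional.

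Three stronger readings are tempting.

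- A reader might infer that a batch shift would bias the PRISM effect. The documents do not support this. Section 11.3 sets permuted blocks within age group and site, CTRA comes from one site, and both arms share one draw schedule. Arms should therefore be roughly balanced over calendar time, and the contrast would mainly gain noise. A chance imbalance in a small sample is possible, but nothing quantifies it.
- A reader might infer that batch was left out of every CTRA model. The covariate list in 11.5.4 belongs only to the model of CTRA against transplant outcomes. Within-patient CTRA change is not defined there, and paired tests are named only generically. The pooled median split is the analysis most clearly exposed.
- A reader might want batch as one extra model term. With about 5 to 9 levels in a small optional single-site sample, a fixed factor is not cheap.

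The split share also depends on assumed uptake and on two conflicting enrolment figures. The simulation further assumes even accrual over 36 months, whereas the change log shows that CTRA was added in October 2019 and that accrual was limited during the pandemic. What survives is that the rule counts tubes and that nothing in the plan prevents the split.

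**Conclusion.** The point holds in conditional form. The shipping rule would put the baseline and 3-month samples of about a quarter to three quarters of participants in different shipments at 50% to 100% uptake, and of about 11% to 21% at 25%. If shipments are processed as separate batches, within-patient CTRA change and the pooled median classification would partly measure batch. The documents leave that condition open, and they give no basis for sizing the resulting error.

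The consequence is limited to an exploratory, optional, single-site outcome. No primary or secondary conclusion depends on it. The change is worth making because it is nearly free, not because the trial's main result is at risk.

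**What to change.** Amend section 9.9.2 so that a participant's tubes are held until the last planned sample is collected or the participant leaves the study, and are then shipped, library-prepared and sequenced together, with both arms in each shipment where possible. Because 20 is not a multiple of 3, a trigger in completed patients is simpler: 7 full series make 21 tubes. This removes batch from within-patient change by design.

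Record the library-preparation and sequencing batch of every sample. In section 11.5.4, state how between-patient CTRA analyses will allow for batch in a parsimonious way, for example batch-centred scores, a within-batch median or a random batch effect, rather than a many-level fixed factor. If the core already pools all shipments into one run, one sentence saying so would meet most of the concern. If some tubes have already been run, recording batch and allowing for it is still useful.

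The cost is longer temporary storage and later results. The oldest tube would wait roughly 3 months more: about 4.0 + 3 = 7.0 to 7.3 + 3 = 10.3 months at full uptake, against the anticipated limit of under 6 months. The storage wording in 9.9.2 should be changed to match. Section 19 plans no return of CTRA results to participants and no interim use of them is described, so the delay should do little harm.
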